7.2.2.2. Dose Reductions

Olaratumab

Olaratumab dose can be reduced to a lower dose to either 12 or 10 mg/kg (15 mg/kg if the toxicity occurs during Cycle 1 of Cohort 3 in Part A), in accordance with the general guidelines shown in Section 7.2.2.3. Once the dose of olaratumab is reduced, re-escalation to the prior dose level is not permitted.

Doxorubicin (Part A)

Dose reduction between cycles in Cohort 1, 2 and 3

Doxorubicin dose can be reduced to a lower dose in accordance with the general guidelines shown in Section 7.2.2.4. Once the dose of doxorubicin is reduced, re-escalation to the prior dose level is not permitted.

Dose reduction within a cycle in Cohort 1

In principle, doxorubicin must be administered on Day 1/2/3 consecutively. No breaks between these administration days are allowed; that is, dose reduction within a cycle is not permitted. The dose must remain constant over these 3 days. In the case that doxorubicin on Day 2/3 or Day 3 cannot be administered due to doxorubicin-related toxicity (or any other reasons), those administrations should be omitted. If a patient recovers from the toxicity sufficiently, and then doxorubicin administration can be resumed, a lower dose than the prior dose level must be selected in accordance with the general guidelines shown in Section 7.2.2.4. However, if the investigators judge that the dose reduction is unnecessary, the dose does not to be reduced in the case that the investigators and the sponsor agree.

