Investigational Product, Dosage, and Mode of Administration or Intervention:**Part A**

- Cohort 1: 15 mg/kg of olaratumab on Day 1 and Day 8, and 25 mg/m² of doxorubicin on Day 1, Day 2, and Day 3 of every 21-day cycle.
- Cohort 2: 15 mg/kg of olaratumab on Day 1 and Day 8, and 75 mg/m² of doxorubicin on Day 1 of every 21-day cycle.
- Cohort 3: 20 mg/kg loading dose of olaratumab on Day 1 and Day 8 in Cycle 1, followed by 15 mg/kg on Day 1 and Day 8 in subsequent cycles, and 75 mg/m² of doxorubicin on Day 1 of every 21-day-cycle.

Part B

This part consists of 1 dose level: 15 mg/kg of olaratumab on Day 1 and Day 8 of every 21-day cycle.

Planned Duration of Treatment:

Patients will be on treatment until one of the discontinuation criteria is met.

Treatment period: 21 days/cycle

Follow-up Period: 28 days

Criteria for Evaluation:

Safety: Dose-limiting toxicities, treatment-emergent adverse events (TEAEs) using Common Terminology Criteria for Adverse Events (CTCAE) version 4.03 and the Medical Dictionary for Regulatory Activities (MedDRA), laboratory evaluations, vital signs, electrocardiograms and cardiac function as measured by echocardiogram.

Bioanalytical: Serum concentrations of olaratumab (Part A and B) and plasma concentrations of doxorubicin (Part A).

Pharmacokinetics: The primary parameters for analysis will be maximum observed concentration (C_{max}) and area under the concentration-time curve (AUC) from time 0 to the last time point with a measurable concentration, and AUC from time 0 to infinity of olaratumab and doxorubicin. Other noncompartmental parameters, such as half-life, clearance, and volume of distribution, may be reported.

Efficacy: Antitumor activity according to Response Evaluation Criteria in Solid Tumors version 1.1.

Biomarkers: Biomarkers related to the mechanism of olaratumab, the PDGF signaling pathway, and the pathobiology of cancer.

Statistical Methods:

Safety: Dose-limiting toxicities will be listed and summarized by frequency. Adverse events (AEs), including TEAEs, will be listed and summarized in frequency tables using MedDRA. Severity of AEs will be classified using CTCAE version 4.03. Other safety data, such as laboratory tests, echocardiography, and vital signs, will be listed and summarized, if appropriate.

Efficacy: Efficacy data will be listed. Also, efficacy data will be summarized using frequency table or summary statistics, depending on the characteristics of the data.

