7.2.1.1. Olaratumab

With the exception of the 20 mg/kg loading dose of olaratumab on Days 1 and 8 in Cycle 1 of Cohort 3, all patients will receive 15 mg/kg of olaratumab on Days 1 and 8 of each 21 day treatment cycle, administered as an intravenous infusion over approximately 60 minutes, until progressive disease or meeting the other discontinuation criteria. Patients enrolled in Part A can be hospitalized for the first 8 days in Cycle 1, according to routine institutional practice.

The dose of olaratumab is dependent upon the patient's weight in kilograms. A change of weight $\geq 10\%$ (increase or decrease) from baseline will result in re-calculation of olaratumab dose to be administered.

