If olaratumab is not administered for more than 21 days from Day 1 of the following scheduled cycle due to an olaratumab related-toxicity that does not resolve, or if more than 2 toxicity-related olaratumab dose reductions are required, treatment with olaratumab will be permanently discontinued.

In the case that doxorubicin is delayed or omitted for any reason (including AEs), administration of olaratumab will continue according to the original schedule. If doxorubicin is not administered for more than 21 days from Day 1 of the following scheduled cycle due to a doxorubicin-related toxicity that does not resolve, treatment with doxorubicin will be permanently discontinued.

If both doxorubicin and olaratumab are discontinued, the patient will be discontinued from the study.

Part B

Day 1 of each cycle (Cycle 2 and beyond) is defined as the 21st day after the first olaratumab administration in the previous cycle.

When olaratumab is not administered on the scheduled day, study therapy will resume provided resolution of the event(s) causing the delay. Dose delay of olaratumab on Day 8 is allowed until 7 days before Day 1 of the following cycle. If olaratumab is discontinued, the patient will be discontinued from the study.

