7.2.2.3. Guidelines for Olaratumab Dose Reduction

7.2.2.3.1. *Hematologic Toxicity*

For Grade ≤ 2 hematologic toxicity, no dose modification is required. For Grade 3 toxicity not adequately controlled with appropriate supportive care (including hematopoietic growth factors, if indicated), olaratumab should not be administered until toxicity \leq Grade 2, or has returned to pretreatment baseline; at this time, dose should be reduced to 12 mg/kg and treatment resumed. In the case of Grade 4 hematologic toxicity associated with olaratumab, olaratumab should not be administered until toxicity is \leq Grade 2, then dose should be reduced to 10 mg/kg and treatment should resume.

7.2.2.3.2. *Nonhematologic Toxicity*

Specific guidelines for dose reduction in patients who experience infusion-related reactions while receiving treatment with olaratumab are found in Section 8.1.3.4.

General guidelines for dose modification for other nonhematologic toxicities related to olaratumab are shown in Table JGDK.7.2.

Table JGDK.7.2. General Guidelines for Dose Modification Due to Nonhematologic Toxicities Related to Olaratumab

Reaction Grade	Required Dose Modification
Grade 1	No dose modification is required.
Grade 2	At the investigator's discretion, the patient may continue to receive olaratumab per protocol, provided that the event does not pose a serious health risk or is easily treated. If necessary, the patient may be dose reduced up to 2 dose reductions (to 12 mg/kg and subsequently to 10 mg/kg) during the study.
Grade 3	For a Grade 3 toxicity not adequately controlled with appropriate supportive care, the dosing must not be administered until toxicity is \leq Grade 1 or has returned to pretreatment baseline; treatment may then resume at a reduced dose of 12 mg/kg (15 mg/kg if the toxicity occurs during Cycle 1 of Cohort 3 in Part A). If toxicity recurs after therapy resumes, a second dose reduction (to 10 mg/kg) is permitted. If more than 2 toxicity-related olaratumab dose reductions are required, treatment with this agent will be permanently discontinued.
Grade 4	The dose must not be administered until dose toxicity is \leq Grade 1 or has returned to baseline. Treatment may then resume with the dose reduced to 10 mg/kg (15 mg/kg if the toxicity occurs during Cycle 1 of Cohort 3 in Part A). If toxicity recurs after therapy resumes, olaratumab treatment will be discontinued.

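### For Cohort 3 Cycle 1, the olaratumab reduction rules give different doses for the same event, and do not say whether a move to the already planned 15 mg/kg counts as a reduction

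*Protocol*

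**What the plan says.** **Planned dose.** The Synopsis and Section 6.2 give Cohort 3 a "20 mg/kg loading dose of olaratumab on Day 1 and Day 8 in Cycle 1, followed by 15 mg/kg" on the same days of later cycles. Section 7.2.1.1 agrees: apart from that loading dose, "all patients will receive 15 mg/kg of olaratumab on Days 1 and 8 of each 21 day treatment cycle".

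**General reduction rule (Section 7.2.2.2).** The levels are 12 or 10 mg/kg, with this exception: "15 mg/kg if the toxicity occurs during Cycle 1 of Cohort 3 in Part A), in accordance with the general guidelines". The exception names no type of toxicity. The sentence refers to the guidelines in Section 7.2.2.3, and the next one bars re-escalation.

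**Hematologic rule (Section 7.2.2.3.1).** For Grade 3 toxicity that supportive care does not control, dosing is held until recovery, and "at this time, dose should be reduced to 12 mg/kg and treatment resumed". For Grade 4 toxicity associated with olaratumab, dosing is held, "then dose should be reduced to 10 mg/kg and treatment should resume". Neither sentence mentions Cohort 3.

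**Nonhematologic rule (Table JGDK.7.2).**
- Grade 2: if necessary, "the patient may be dose reduced up to 2 dose reductions (to 12 mg/kg and subsequently to 10 mg/kg) during the study". There is no Cohort 3 exception.
- Grade 3: 12 mg/kg, or 15 mg/kg in Cohort 3 Cycle 1, with a second reduction to 10 mg/kg on recurrence.
- Grade 4: 10 mg/kg, or 15 mg/kg in Cohort 3 Cycle 1, with olaratumab stopped on recurrence.

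**Limit (Section 7.2.2.1, repeated in the Grade 3 row).** "if more than 2 toxicity-related olaratumab dose reductions are required, treatment with olaratumab will be permanently discontinued".

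**The concern.** Section 7.2.2.2 and the guidelines it points to should lead a site to the same dose. For a Cohort 3 patient with a qualifying hematologic toxicity in Cycle 1 they do not, and two sites could treat the same event differently while each followed the protocol. Because re-escalation is barred, the difference lasts as long as the patient stays on olaratumab.

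The second issue is what the word reduction means in a cohort whose planned dose falls after Cycle 1 anyway. A patient who has had both loading doses is due 15 mg/kg next. If a toxicity then leads to a so-called reduction to 15 mg/kg, the patient receives the planned dose. Whether one of two permitted reductions has been spent decides how close that patient is to mandatory discontinuation of olaratumab. It also decides whether the event belongs among the treatment reductions that protocol Section 10.4 summarizes and SAP Section 6.11.1 lists.

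**Working it through.** No sample-size or power figure is involved. The check sets the rules side by side for a patient on 20 mg/kg in Cohort 3 Cycle 1, then counts reductions.

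**Step 1. Dose each rule gives**

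| Event in Cohort 3 Cycle 1 | Section 7.2.2.2 | Section 7.2.2.3.1 or Table JGDK.7.2 | Same dose? |
|---|---|---|---|
| Hematologic Grade 3, not controlled | 15 mg/kg | 12 mg/kg | No |
| Hematologic Grade 4, olaratumab-associated | 15 mg/kg | 10 mg/kg | No |
| Nonhematologic Grade 2, if reduced | 15 mg/kg | 12 mg/kg, then 10 mg/kg | No |
| Nonhematologic Grade 3 | 15 mg/kg | 15 mg/kg | Yes |
| Nonhematologic Grade 4 | 15 mg/kg | 15 mg/kg | Yes |

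The disagreement is confined to the hematologic rule and the nonhematologic Grade 2 row. Read literally, the table also takes a nonhematologic Grade 2 event to a lower dose (12 mg/kg) than a Grade 3 or 4 event (15 mg/kg).

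**Step 2. Size of the difference**
- Relative to the 20 mg/kg loading dose: 15 is (20 − 15)/20 = 25% lower; 12 is (20 − 12)/20 = 40% lower; 10 is (20 − 10)/20 = 50% lower.
- Between the two rules: 12/15 = 0.80, a 20% lower dose; 10/15 = 0.67, a 33% lower dose.

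**Step 3. Is 15 mg/kg a reduction?**
- Toxicity before the Day 8 dose: that dose was planned at 20 mg/kg, so 15 mg/kg is a real 25% reduction.
- Toxicity after the Day 8 dose: the next planned dose is 15 mg/kg, so the change from plan is (15 − 15)/15 = 0%. The row is not empty even then, because dosing must still be held until recovery.

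**Step 4. The limit of two**
- If the move to 15 mg/kg counts, 2 − 1 = 1 reduction remains.
- If it does not count, 2 − 0 = 2 remain.

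Neither Section 7.2.2.1, Section 7.2.2.2 nor the table says which applies. The SAP cannot settle it either: it was written to the December 2014 protocol (SAP Section 3) and describes only Cohorts 1 and 2 (SAP Section 5.1).

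**The case against.** The best reply is that Section 7.2.2.2 merely lists the available dose levels and defers to Section 7.2.2.3, which confines the 15 mg/kg level to nonhematologic Grades 3 and 4. That is a possible reading. But the exception in Section 7.2.2.2 is then worded too broadly for hematologic toxicity and for nonhematologic Grade 2, so the text needs changing on either reading.

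A second reply is that few patients are affected, and this stands in part. The Grade 3 hematologic rule applies only when supportive care fails, and the Grade 4 rule only when the event is associated with olaratumab. Section 7.2.2.1 says olaratumab is not altered for doxorubicin-related toxicity, and Section 5.1 counts neutropenia among the known doxorubicin toxicities. Section 5.2.2 says Amendment (b) followed the collection of enough data for the primary and secondary objectives, which suggests, without proving, that few Cohort 3 Cycle 1 decisions remained.

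On the count, the Grade 3 row calls the step to 10 mg/kg on recurrence a second reduction. This hints that the step before it was the first, but the row does not say so for a move to a dose already planned.

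A reader might also infer that Amendment (a) inserted the exception in some places and overlooked others. The documents do not show this. Section 5.2.1 says only that Cohort 3 was added, and the change summary supplied covers Amendment (b).

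**Conclusion.** The rules are inconsistent as written for Cohort 3 Cycle 1. The same qualifying hematologic event leads to 15 or 12 mg/kg (Grade 3), or to 15 or 10 mg/kg (Grade 4). The nonhematologic Grade 2 row has the same gap, 15 against 12 mg/kg. Separately, after the Day 8 loading dose a patient moved to 15 mg/kg has either one or two reductions left, and the text does not say which. This rests on reading the exception in Section 7.2.2.2 as it stands, without a limit by toxicity type, and on the conditions in Section 7.2.2.3.1 being met. The documents do not show how many patients were affected.

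Two stronger conclusions are tempting and not supported.
- **Three reduction steps against a limit of two.** The levels 15, 12 and 10 mg/kg do lie below 20, but no row prescribes that sequence. The Grade 3 row gives 20 to 15 to 10, which is two steps. The Grade 4 row gives 15 and then discontinuation.
- **A changed count of dose-limiting toxicities.** Section 7.2.1.3 includes toxicities that require a reduction during Cycle 1. Before Day 8, all of 15, 12 and 10 mg/kg are below 20, so the choice between them does not affect that criterion. After Day 8 the next dose normally falls in Cycle 2, unless Day 8 was delayed. No effect on the Cohort 3 tolerability decision is shown.

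**What to change.** Reconcile Section 7.2.2.2, Section 7.2.2.3.1, Table JGDK.7.2 and the two-reduction limit so that a single rule applies to each Cohort 3 Cycle 1 event. The text should state:
- whether the Cycle 1 exception covers hematologic toxicity and nonhematologic Grade 2 toxicity;
- whether a move to the already planned 15 mg/kg counts as a reduction toward the discontinuation limit;
- whether the same move is recorded as a reduction in the listing of treatment reductions, with a matching Cohort 3 convention in the SAP.

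Which dose and which rule apply is for the sponsor to decide. The cost is protocol wording and a line in the SAP; no design, sample size or data collection changes.

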7.2.2.3. Guidelines for Olaratumab Dose Reduction

7.2.2.3.1. *Hematologic Toxicity*

For Grade ≤ 2 hematologic toxicity, no dose modification is required. For Grade 3 toxicity not adequately controlled with appropriate supportive care (including hematopoietic growth factors, if indicated), olaratumab should not be administered until toxicity \leq Grade 2, or has returned to pretreatment baseline; at this time, dose should be reduced to 12 mg/kg and treatment resumed. In the case of Grade 4 hematologic toxicity associated with olaratumab, olaratumab should not be administered until toxicity is \leq Grade 2, then dose should be reduced to 10 mg/kg and treatment should resume.

7.2.2.3.2. *Nonhematologic Toxicity*

Specific guidelines for dose reduction in patients who experience infusion-related reactions while receiving treatment with olaratumab are found in Section 8.1.3.4.

General guidelines for dose modification for other nonhematologic toxicities related to olaratumab are shown in Table JGDK.7.2.

Table JGDK.7.2. General Guidelines for Dose Modification Due to Nonhematologic Toxicities Related to Olaratumab

Reaction Grade	Required Dose Modification
Grade 1	No dose modification is required.
Grade 2	At the investigator's discretion, the patient may continue to receive olaratumab per protocol, provided that the event does not pose a serious health risk or is easily treated. If necessary, the patient may be dose reduced up to 2 dose reductions (to 12 mg/kg and subsequently to 10 mg/kg) during the study.
Grade 3	For a Grade 3 toxicity not adequately controlled with appropriate supportive care, the dosing must not be administered until toxicity is \leq Grade 1 or has returned to pretreatment baseline; treatment may then resume at a reduced dose of 12 mg/kg (15 mg/kg if the toxicity occurs during Cycle 1 of Cohort 3 in Part A). If toxicity recurs after therapy resumes, a second dose reduction (to 10 mg/kg) is permitted. If more than 2 toxicity-related olaratumab dose reductions are required, treatment with this agent will be permanently discontinued.
Grade 4	The dose must not be administered until dose toxicity is \leq Grade 1 or has returned to baseline. Treatment may then resume with the dose reduced to 10 mg/kg (15 mg/kg if the toxicity occurs during Cycle 1 of Cohort 3 in Part A). If toxicity recurs after therapy resumes, olaratumab treatment will be discontinued.

7.2.2.4. Guidelines for Doxorubicin Dose Reduction (Part A)

7.2.2.4.1. Hematologic Toxicity

Doxorubicin will not be administered if the patient's ANC is <1000 cells/mm 3 or if the platelet count is $<100,000$ cells/mm 3 . When necessary, the next treatment cycle should be delayed until the ANC is ≥1000 cells/mm 3 and the platelet count is $\geq100,000$ cells/mm 3 . See [Table JGDK.7.3](#) for doxorubicin dose reduction for neutropenia.

Table JGDK.7.3. General Guidelines for Doxorubicin Dose Reduction Due to Neutropenia

Toxicity	Required Dose Modification	
	Cohort 1 (25 mg/m 2 on Day1/2/3)	Cohort 2 and 3 (75 mg/m 2 on Day1)
\geq Grade 3 neutropenic fever/infection	Approximately 60 mg/m 2 (20 mg/m 2 on Day 1/2/3)	Approximately 60 mg/m 2
Grade 4 neutropenia lasting longer than 7 days	Approximately 60 mg/m 2 (20 mg/m 2 on Day 1/2/3)	Approximately 60 mg/m 2
Second incidence of either: 1) \geq Grade 3 neutropenic fever/infection 2) Grade 4 neutropenia lasting longer than 7 days	Second level of dose reduction to 45 mg/m 2 (15 mg/m 2 on Day 1/2/3)	Second level of dose reduction to 45 mg/m 2

7.2.2.4.2. Nonhematologic Toxicity

In the case of hyperbilirubinemia and elevated AST, dose reduction of doxorubicin should be considered. See [Table JGDK.7.4](#) for doxorubicin dose reduction for hyperbilirubinemia and elevated AST.

Table JGDK.7.4. General Guidelines for Doxorubicin Dose Reduction Due to Hyperbilirubinemia and Elevated AST

Serum bilirubin concentration (mg/dL)	AST (IU/L)	Required Dose Reduction (Cohort 1, 2 and 3)
1.5 to 3.0	or, 60 to 180	50%
3.1 to 5.0	or, >180	75%
>5.0	-	Discontinuation

Abbreviation: AST = aspartate aminotransferase.

7.2.2.4.3. Cardiovascular

Electrocardiogram changes, arrhythmias, tachycardia, and/or chest pain should be managed based on the specific findings.

Patients will undergo baseline LVEF determination by echocardiogram. This evaluation may be repeated at any time during the study if clinically indicated. If an echocardiogram conducted on study indicates a resting LVEF is <50%, then the echocardiogram should be repeated for monitoring. If there is an absolute decrease in LVEF of >20% from the previous evaluation, or if the actual LVEF decreases to ≤40%, then doxorubicin should be discontinued. Doxorubicin should also be discontinued if the patient develops Grade 3 or 4 left ventricular systolic dysfunction (symptomatic congestive heart failure).

7.3. Method of Assignment to Treatment

Patients who meet all criteria for enrollment will be assigned to receive olaratumab in combination with doxorubicin (Cohort 1, 2 or 3 in Part A) or olaratumab monotherapy (Part B), at the investigator's discretion. Before each patient's enrollment into the study, an eligibility check must be conducted at the investigational site to confirm that each patient meets all enrollment criteria. Upon confirmation of eligibility, the sponsor or designee will confirm the dose and identification number assignment for each patient. For initiation of Cohort 2 and 3, refer to Section 7.2.1.4.

7.4. Blinding

This is an open-label study.

7.5. Concomitant Therapy

No other chemotherapy, immunotherapy, radiation therapy, hormonal cancer therapy, surgery for cancer, or experimental medications will be permitted while patients are participating in this study.

Patients must receive full supportive care therapies concomitantly during the study, including antiemetic treatment as per institutional guidelines. Granulocyte colony stimulating factors (G-CSF) may be used in accordance with American Society of Clinical Oncology (ASCO) guidelines (Smith et al. 2006), and if they adhere to the dosage and administration described in the Japan Package Insert. Granulocyte colony stimulating factor treatment as the primary prophylaxis is not permitted and pegfilgrastim are not permitted. Granulocyte colony

stimulating factors must be discontinued at least 24 hours before beginning the next cycle of treatment.

Appropriate documentation for all forms of premedications, supportive care, and concomitant medications (eg, medications such as sedatives, antibiotics, analgesics, antihistamines, corticosteroids, erythropoietin; procedures such as paracentesis, thoracentesis; blood products such as blood cells, platelets, fresh frozen plasma transfusions) must be captured on the electronic case report form (eCRF). Erythropoietin/blood product use and platelet transfusions may be used in accordance with ASCO guidelines (Schiffer et al. 2001; Rizzo et al. 2010).

7.6. Treatment Compliance

Olaratumab and doxorubicin (Part A) or olaratumab (Part B) will be administered at the investigational sites, under the direction of the investigator. As a result, a patient's compliance with study drug administration is ensured. Patients should attend scheduled clinic visits and must comply with study criteria under their control. Deviation(s) from the prescribed dosage regimen should be recorded on the CRF.

8. Safety, Pharmacokinetic, and Efficacy Data Collection

